#### 14.3 Exploratory objectives

#### « Exploratory objectives 1, 2, 3 and 4 are stratifications to the co-primary objectives.»

- To estimate brand-specific CVE against hospitalisation due to laboratory-confirmed SARS-CoV-2 in severe acute respiratory infection (SARI) patients who have been vaccinated with at least 1 COVID-19 vaccine dose, compared to unvaccinated patients,
  - by severity level .
  - by calendar time .
- To estimate brand-specific CVE against hospitalisation due to laboratory-confirmed SARS-CoV-2 in SARI patients who completed a primary series vaccination, compared to unvaccinated patients,
  - by severity level .
  - by calendar time .
- 3. To estimate brand-specific CVE against hospitalisation due to laboratory-confirmed SARS-CoV-2 in SARI patients who previously completed a primary series with any COVID-19 vaccine and have received at least one additional COVID-19 vaccine dose , compared to (1) unvaccinated patients and to (2) patients who previously completed a primary series with any COVID-19 vaccine but who did not receive the last additional dose of interest ,
  - by severity level .
  - by calendar time .
- 4. [Only to support the interpretation of exploratory objective 3 ]: To estimate CVE across brands against hospitalisation due to laboratory-confirmed SARS-CoV-2 in SARI patients who previously completed at least a primary series with any COVID-19 vaccine but who did not receive the last additional dose of interest , compared to unvaccinated patients,
  - by severity level .
  - by calendar time .
- 5. To estimate the brand-specific effect of COVID-19 vaccination in patients who have [been vaccinated with at least 1 COVID-19 vaccine dose-- completed primary series vaccination] on length of hospital stay (in days) due to laboratory-confirmed SARS-CoV-2 admission compared with patients who [are unvaccinated have been vaccinated with at least 1 COVID-19 vaccine dose ...].
- 6. To study the potential occurrence of VAED by describing the clinical and laboratory features of critical COVID-19 disease  cases, by COVID-19 vaccine exposure status and time since vaccination. 

 Throughout the protocol, additional dose refers to booster doses (1st, 2nd, 3rd...). COVID-19 vaccine dose will be classified as primary (P) or additional dose (N) by expert consensus.

 Patients who did not receive the last additional dose received one dose less (P+N-1) compared to the patients who received one additional dose of the vaccine of interest (P+N), further explanation can be found in section 15.14.4.

 The SARI patients used for the supporting objective are exactly the same patients as the ones used for the comparator groups of the supported objective.

 Only estimated if the type includes at least two brands or only the brand of interest.

 Three mutually exclusive categories: (a) hospital admission without intensive care unit (ICU) admission and without in-hospital death, (b) ICU admission without in hospital death and (c) in-hospital death.

 Calendar time at date of hospital admission as a proxy for changing genetic variants of the SARS-CoV-2 virus.

 The text between square brackets needs to be selected to match the exposure definitions from the co-primary objectives.

 Critical COVID-19 disease is defined as being admitted to ICU due to laboratory-confirmed SARS-CoV-2.

 It is postulated that the potential VAED risk may change with waning vaccine-induced immunity, hence with time since vaccination as a proxy.

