# **15.8 Exposure (COVID-19 vaccination)**

#### 15.8.1 Exposure definitions

#### « Exposure outcomes to be aligned with study objectives. »

- 1. Vaccinated with at least one dose: vaccinated with **at least 1 dose** of the COVID-19 vaccine brand of interest  > 14 days prior to SARI symptom onset.
- 2. Completed primary series vaccination: **completed a primary series** with the COVID-19 vaccine brand of interest  > 14 days prior to SARI symptom onset.

- At least one additional COVID-19 vaccine dose: any COVID-19 vaccine dose with the brand of interest  given as last dose > 14 days prior to SARI symptom onset to subjects who previously completed a primary series with any COVID-19 vaccine(s) .
- 4. Previously vaccinated but did not receive the last additional dose of interest: previously completed at least a primary series with any COVID-19 vaccine prior to SARI symptom onset, and was **eligible**  **to receive the last additional dose of interest but did not receive it**.
- Recently vaccinated: vaccinated with any COVID-19 vaccine <= 14 days prior to SARI symptom onset .
- 6. Unvaccinated: did **not receive any COVID-19 vaccine dose.**
- 7. Other: additional vaccine exposure case definitions might be defined depending on the reallife use of the COVID-19 vaccines.

 *The COVID-19 vaccine with brand of interest must be EMA approved.* 

 Throughout the protocol, additional dose refers to booster doses (1st, 2nd, 3rd...). COVID-19 vaccine dose will be classified as primary (P) or additional dose (N) by expert consensus.

 For its secondary objective, the Study Requestor may define specific exposures based on the number of COVID-19 vaccine doses and type(s) of the COVID-19 vaccine doses given prior to the last dose.

 at least 3 months since last dose.

 Recently vaccinated patients will not be considered protected by the last vaccine dose. Their data use will be specified in the statistical analysis plan. This applies to both primary series and additional doses.

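### Exploratory objective 5 lists a length-of-stay comparator that, as defined, contains the exposed groups it would be compared with

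*Protocol*

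**What the plan says.** Exploratory objective 5 in section 14.3 asks for the brand-specific effect of vaccination on length of stay among admissions with laboratory-confirmed SARS-CoV-2. It has two brackets.

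- **Exposed group:** "been vaccinated with at least 1 COVID-19 vaccine dose-- completed primary series vaccination". The abstract has the same two options in slightly different words and leaves its list open-ended.
- **Comparator:** "compared with patients who [are unvaccinated have been vaccinated with at least 1 COVID-19 vaccine dose". This list is open-ended in both places.

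Footnote 7, marked on the exposed-group bracket, gives the selection rule: "The text between square brackets needs to be selected to match the exposure definitions from the co-primary objectives".

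Section 15.8.1 defines the exposures, each counted only if given more than 14 days before symptom onset:

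- Definition 1, "Vaccinated with at least one dose": "vaccinated with at least 1 dose of the COVID-19 vaccine brand of interest".
- Definition 2, "Completed primary series vaccination": "completed a primary series with the COVID-19 vaccine brand of interest".
- Definition 3, an additional dose of the brand of interest, "given as last dose > 14 days prior to SARI symptom onset to subjects who previously completed a primary series with any COVID-19 vaccine(s").

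The co-primary objectives in section 14.1 use two comparators: unvaccinated patients, and patients with one dose fewer than the exposed (P+N-1).

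**The concern.** A contrast between two groups needs groups that do not share members. Definition 1 sets a minimum number of doses and no maximum. It does not exclude patients who went on to complete the series or to receive a booster, and nothing else in the protocol removes exposed patients from this comparator. A team that takes the listed option at face value would therefore set an exposed group against a set containing that same group.

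What is at stake is the meaning of the length-of-stay estimate in any derived protocol that uses the option. Depending on the pairing, the estimate is undefined or understates the difference between the exposed patients and the vaccinated patients outside that group. The section on the background of the master protocol says that the document exists to harmonise objectives and exposures across studies, so a faulty listed option can be carried into several of them.

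**Working it through.** The protocol states no effect size, sample size or power for length of stay, so there is no figure of its own to reproduce. Two checks apply.

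**1. Do the groups overlap?** The definitions in section 15.8.1, set side by side:

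- A patient in definition 2 has completed a series of the brand of interest more than 14 days before onset. That patient has at least one such dose and is in definition 1.
- A patient in definition 3 has the brand of interest as last dose more than 14 days before onset, and is also in definition 1.
- Definition 1 is identical to itself.

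The comparator bracket does not name a brand. Read through definition 1, it means the brand of interest. Read as any brand, the group is larger and still contains all three. The overlap holds either way.

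The co-primary comparators do not have this property. An unvaccinated patient has no dose, and a P+N-1 patient lacks the dose that defines the exposed group.

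**2. What does the overlap do to an estimate?** Let E be the exposed group, C the comparator as written, R the members of C who are not in E, and f the share of C made up of E. For mean length of stay:

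mean(C) = f × mean(E) + (1 − f) × mean(R)

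mean(E) − mean(C) = (1 − f) × [mean(E) − mean(R)]

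The difference as written is the non-overlapping difference multiplied by 1 − f. The values of f below are assumptions, chosen to show the range:

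| f | Fraction of the difference kept, 1 − f |
|---|---|
| 10% | 90% |
| 25% | 75% |
| 50% | 50% |
| 75% | 25% |
| 90% | 10% |
| 100% | 0 |

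The last row is the pairing of at least one dose with at least one dose of the same brand. There R is empty, so no contrast exists.

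**Why f cannot be read from the protocol.** Objective 5 concerns laboratory-confirmed cases. The brand shares in section 15.11.1.1 (10% to 75%) are shares of vaccination coverage among controls, as Annex 6 confirms by conditioning on control status. No series-completion share is given at all. A share in controls does not carry over to cases. Suppose 90% of those who start the series complete it among controls (assumed), effectiveness is 80% for a completed series (one of the planning values) and 50% for a partial one (assumed). Then among cases

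f = (0.9 × 0.2) / (0.9 × 0.2 + 0.1 × 0.5) = 0.18 / 0.23 = 0.78,

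not 0.90, and the fraction kept is 22% rather than 10%. The direction is fixed by the algebra. The size depends on inputs that the protocol does not hold.

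**The case against.** The strongest reply is that nothing has been fixed. The title page says that bracketed text is to be completed, section 14.1 lets study teams select and modify objectives, the comparator list is open-ended, and unvaccinated patients are the first option. This stands, and it limits the severity. A reader might infer that the study plans to compare a group with itself. It does not: the problem arises only if a team picks this option and leaves it undefined. The option is nevertheless listed, and as listed it is wrong.

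A second reply is that the brackets may be meant to be read in step: at least one dose against unvaccinated, then completed series against those who started but did not complete. That would be a sensible contrast between separate groups. The separators between options are partly lost in the text as read, so this cannot be ruled out. But the words do not restrict the comparator to incomplete series, and definition 1 does not either.

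A third concerns footnote 7. A reader might infer that the option violates it, because no co-primary objective compares against at least one dose. The footnote does not support that. It is marked on the exposed-group bracket and asks only for a match to co-primary exposure definitions, of which at least one dose is one. By the same token, the footnote does not prevent the overlap.

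A fourth is that the dilution factor, and any claim that confidence intervals would be wrong because records are shared, presuppose an unadjusted difference in means with patients entered on both sides. This also stands. A regression with one exposure category per patient has no duplicates. The length-of-stay model is properly left to the statistical analysis plan, so the factor is conditional and no claim is made about the intervals.

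**Conclusion.** The point holds in a limited form. The at-least-one-dose comparator in exploratory objective 5 contains both exposed groups listed in section 14.3, whichever brand reading is used, and no passage removes them. Selected as written, it gives no contrast for at least one dose of the same brand, and a contrast pulled towards zero for a completed primary series.

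For an unadjusted difference in means with the comparator taken literally, the fraction kept is 1 − f. Because the protocol supplies neither f among cases nor an expected difference in stay, a loss in days cannot be derived from it, and any such figure would be an assumption. Severity is the lowest: the objective is exploratory, and the harm depends on a team choosing this option.

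**What to change.** Make the comparator exclude the exposed group, in section 14.3 and in the matching line of the abstract:

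- Exposed group at least one dose: allow only unvaccinated patients as comparator.
- Exposed group completed primary series: allow unvaccinated patients, or patients with at least one dose whose primary series is not completed.
- If an additional-dose exposure is added to this objective: use unvaccinated or P+N-1 patients, as in co-primary objective 3.

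Deleting the at-least-one-dose option outright is unnecessary and would also remove a legitimate comparison of complete with partial vaccination. The cost is one line in each of two places. Section 15.8.2 already requires information on all prior doses, so the narrower group can be identified without new data or patients.

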#### 15.9.4 Critical COVID-19 disease

A critical COVID-19 disease case is defined as a COVID-19 disease case being admitted to the ICU. The clinical and laboratory characteristics of the critical COVID-19 disease cases will be described (Annex 1).

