care facilities, healthcare workers, social care personnel and persons with certain comorbidities [28]. The presence of such vaccination priority groups is an important potential source of confounding in COVID-19 vaccine effectiveness studies. In addition, the uptake of vaccination may be highest among individuals who adhered most strongly to NPIs (i.e. subjects exhibiting precautionary health behaviour such as wearing face masks, using hand sanitiser, avoiding public places) and consequently have a lower propensity of natural infection and immunity. As naturally acquired immunity may be strongly protective against re-infection (~90%) [29], lack of precautionary health behaviour (~previous SARS-CoV-2 infection) might be an important potential confounder as well. An alternative bias mechanism might be that subjects feel protected once vaccinated and relax the precautionary health measures that were taken prior to vaccination. In addition, propensity towards vaccination in general might also act as a confounder when, for example, subjects more likely to be vaccinated against COVID-19 are also more likely to be vaccinated against influenza and/or against pneumococcal infection (e.g. as is the case for healthcare workers, risk groups and persons with a positive attitude towards vaccination). Joint vaccination against COVID-19, influenza and/or pneumococcal infection might bias the results of TNCC studies as such joint vaccination will affect both the probability that the subject becomes a case as well as the probability that the subject becomes a control. Another potential important confounder is ethnicity and socio-economic background. It is well established that some minority ethnic groups have a higher risk of confirmed SARS-CoV-2 infection and higher risk of developing critical COVID-19 disease given exposure, even after accounting for socio-economic variables [30]. When these groups are also less likely to be vaccinated, the vaccine effectiveness estimates will be overestimated. Finally, CVE studies are strongly subject to time-varying confounding as both the COVID-19 vaccination coverage and the SARS-CoV-2 infection pressure and virulence will co-vary over time.

Pre-existing immunity is a factor influencing vaccine effectiveness estimates. Prior natural infection is a typical reason for pre-existing immunity, however prior infections may be undocumented. A careful interpretation of all time-related effects will be warranted.

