# 18.3 Informed consent

Written informed consent will be obtained from all participants/guardians as specified by the national/regional ethics committee, if applicable. The following information should be specified in the informed consent form (ICF) (Annex 5): who is responsible for the study, aim of the study, nature of processed data, purposes of processing, purpose of the use of the data including potential future use of the data to advance knowledge on vaccines, recipients of possible data transfers, rights of the study participants, and consequences of not accepting the informed consent. Specific consent procedures may be needed for patients in poor health conditions (e.g. oral witnessed consent, consent by next of kin) or for children (assent). If informed consent will not be required, the reason will be stated.

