# ANNEX 1: VACCINE-ASSOCIATED ENHANCED DISEASE (VAED)

VAEDs are modified and severe presentations of clinical infections affecting individuals exposed to a wild-type pathogen after having received a prior vaccine against the same pathogen [1]. VAED has been observed in the past following administration of measles and RSV vaccines [2]. VAED is a theoretical concern for COVID-19 vaccines, based on observations from other respiratory viruses and from animal models of highly pathogenic coronaviruses [3]. While the underlying potential mechanisms for VAED are unclear, VAED always involves a memory response primed by vaccination and appears to target the same organs as wild-type infections [3]. Particular concerns include the potential for (inactivated whole-virus) vaccines to elicit antibody-dependent enhancement (ADE) of infection or vaccine-associated enhanced respiratory disease (VAERD) upon SARS-CoV-2 infection [4], although neither has been observed in clinical trials so far. Studying VAED on an individual patient level is challenging, as no confirmatory tests to diagnose VAED exist, and distinguishing vaccine failure from VAED among vaccinees is difficult.

VAED may be studied on a population level by comparing the occurrence and presentation of severe disease among vaccinated and non-vaccinated patients. VAED through ADE is postulated to occur with low levels of neutralising antibodies, and where non-neutralising or poorly neutralising antibodies increase the subsequent viral entry into cells, thereby intensifying the infection [5]. The effect of waning antibody titers after vaccination on ADE is unknown [6]. If neutralising antibodies wane over time, an association between time since vaccination and the risk of developing severe disease may be observed. Therefore, CVE should be studied against different levels of COVID-19 disease severity by time since vaccination.

Further information on VAED including possible pathophysiologic pathways is provided by Munoz et al. [3].

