# The following form should be used to capture clinical and laboratory features of patients with critical COVID-19 disease admitted to the ICU.

#### **Section A: clinical features**

Please complete the tables below concerning the patient's condition during ICU stay.

During ICU admission, did th patient have any measurem rest of:		If yes, please provide the following details:
a respiratory rate ≥ 30 per minute?	□ No	
	🗆 Yes	
an oxygen saturation ≤ 93%	🗆 No	
on room air?	🗆 Yes	
a systolic blood pressure	🗆 No	
<pre>< 90 mmHg or a diastolic blood pressure < 60 mmHg?</pre>	□ Yes	
fever $\geq$ 39.3°C?	🗆 No	
	□ Yes	Total number of days:
a heart rate ≥ 125 beats per	🗆 No	
minute?	🗆 Yes	
During ICU admission, did th patient ever require:	e	If yes, please provide the following details:
non-invasive supplemental	🗆 No	
oxygen?	🗆 Yes	Total number of days:
respiratory ventilator	🗆 No	
support or ECMO  ?	🗆 Yes	Total number of days:
treatment with vasopressors?	□ No	
	□ Yes	Total number of days:
-	-	exhibit signs or symptoms of new/worsening dysfunction in
any of the following categorie	5?	
Gastrointestinal disorders		
Acute liver failure	🗆 No	□ Yes
Acute renal failure	🗆 No	□ Yes
Renal replacement therapy	🗆 No	□ Yes
Neurological disorders		

 Extracorporeal membrane oxygenation

						COVIDINIVE
Encephalopathy	🗆 No	🗆 Yes				
Convulsions/seizures	🗆 No	🗆 Yes				
Meningitis	🗆 No	🗆 Yes				
Altered level of	🗆 No	🗆 Yes				
consciousness						
Guillain-Barre Syndrome	🗆 No	🗆 Yes				
Cerebrovascular stroke	🗆 No	🗆 Yes				
Other	🗆 No	🗆 Yes	If yes, specify:			
Respiratory disorders						
Acute respiratory distress	🗆 No	🗆 Yes				
syndrome (ARDS)			If the second states to all			
Pneumonia	🗆 No	□ Yes	If yes, radiological confirmation?	🗆 No	🗆 Yes	
Acute respiratory failure	🗆 No	🗆 Yes	commution:			
Other	🗆 No	🗆 Yes	If yes, specify:			
Cardiac disorders						
Myocardial infarction	🗆 No	🗆 Yes				
Arrhythmia (new onset)	🗆 No	🗆 Yes				
Ischemic heart disease	🗆 No	🗆 Yes				
Myocarditis, pericarditis	🗆 No	🗆 Yes				
Stress cardiomyopathy	🗆 No	🗆 Yes				
Microangiopathy	🗆 No	🗆 Yes				
Other	🗆 No	🗆 Yes	If yes, specify:			
Vascular disorders						
Deep vein thrombosis	🗆 No	🗆 Yes				
Pulmonary embolus	🗆 No	🗆 Yes				
Limb ischemia	🗆 No	🗆 Yes				
Vasculitis	🗆 No	🗆 Yes				
Thrombocytopenia	🗆 No	🗆 Yes				
Other	🗆 No	🗆 Yes	If yes, specify:			
Others						
Multi-organ failure	🗆 No	🗆 Yes	If yes, specify:			
Multisystem inflammatory	🗆 No	🗆 Yes				
syndrome						

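### The VAED objective breaks ICU features down only by vaccine exposure and time since vaccination, so differences in age and comorbidity can appear as, or mask, enhanced disease

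*Protocol*

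**What the plan says.** Objective 6 in Section 14.3 (repeated in the Section 8 abstract) is worded "To study the potential occurrence of VAED by describing the clinical and laboratory features of critical COVID-19 disease" and then "cases, by COVID-19 vaccine exposure status and time since vaccination". Those are the only two breakdown factors. A footnote to the objective makes time since vaccination a stand-in for waning immunity and hence for VAED risk.

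Section 15.9.4 defines the population: "A critical COVID-19 disease case is defined as a COVID-19 disease case being admitted to the ICU". It gives the analysis in one sentence: "The clinical and laboratory characteristics of the critical COVID-19 disease cases will be described (Annex 1". Annex 1 supplies the data form.

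The table is meant to be compared across groups. Section 13 says VAED cannot realistically be assessed case by case and has to be assessed in populations. Annex 1 says it may be studied by comparing how often severe disease occurs, and how it presents, in vaccinated and non-vaccinated patients. It adds that, if antibodies wane, "an association between time since vaccination and the risk of developing severe disease may be observed".

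On who was vaccinated, Section 17 names elderly people and persons with certain comorbidities among the priority groups and concludes: "The presence of such vaccination priority groups is an important potential source of confounding in COVID-19 vaccine effectiveness studies". The limitations in Section 8 add that people at highest risk of severe disease were targeted first.

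Confounder adjustment is stated in 15.14.4.1 for vaccine effectiveness (CVE) and in 15.14.4.3 for relative effectiveness (rVE). Section 15.14.3 describes covariates among cases and controls, not ICU features by exposure.

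**The concern.** By the protocol's own account, both column variables of the VAED table, exposure and time since vaccination, are linked to age and comorbidity. If an ICU feature such as organ failure also varies with age or comorbidity, its prevalence will differ between columns even when the vaccine does nothing to the course of disease. Section 17 recognises this confounding for effectiveness estimates but does not carry it over to the VAED description, which uses the same exposure.

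Because the comparison is between groups, no review of individual cases can correct a misleading table. A false pattern could be taken as a safety signal against a brand, or a real excess could be cancelled out and missed.

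**Working it through.** The protocol states no rate, effect size or sample size for objective 6, so there is no figure to reproduce. The check asks how far a prevalence ratio can move from 1.00 through age mix alone. All feature rates and age shares are assumptions.

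**Step 1: age mix from the protocol's own formula.** Annex 6 generates case exposure from the odds ratio (OR) and the control coverage. With one vaccinated group and coverage c, P(vaccinated | case) = o/(1+o), where o = OR × c/(1−c). CVE of 80% or 90% and coverage of 60%, 80% or 90% come from Section 15.11.1.1. Using those overall coverages as age-specific values, and the same OR in both age groups and for ICU cases, is an assumption.

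Take CVE 80% (OR 0.2), coverage 90% in older and 60% in younger people, and half of ICU cases older:
- Older: o = 0.2 × 0.9/0.1 = 1.8, so P = 1.8/2.8 = 0.643.
- Younger: o = 0.2 × 0.6/0.4 = 0.3, so P = 0.3/1.3 = 0.231.
- Older share of vaccinated ICU cases: 0.643/(0.643 + 0.231) = 73.6%.
- Older share of unvaccinated ICU cases: 0.357/(0.357 + 0.769) = 31.7%.

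**Step 2: ratio with no VAED.** Let v and u be the older shares in vaccinated and unvaccinated ICU cases. Ratio = [v × p_old + (1−v) × p_young] / [u × p_old + (1−u) × p_young].
- Feature in 40% of older and 20% of younger cases: 0.347/0.263 = 1.32.
- Gradient reversed (20% older, 40% younger): 0.253/0.337 = 0.75. A true within-age ratio of 1.30 then shows as 1.30 × 0.751 = 0.98.

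**Step 3: range.** The grid was CVE 80% and 90%; coverage pairs 90/80, 80/60 and 90/60; and 30%, 50% or 70% of ICU cases older.

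| Feature prevalence, older/younger | Ratio with no VAED |
|---|---|
| 30%/20% or 40%/20% (rises with age) | 1.06 to 1.33 |
| 20%/40% (falls with age) | 0.75 to 0.91 |
| Equal at all ages, or equal coverage at all ages | 1.00 |

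**Step 4: age shares assumed directly.**
- Shares 80%/40%, feature 50%/20%: 0.44/0.32 = 1.38.
- Shares 70%/50%, feature 50%/20%: 0.41/0.35 = 1.17.
- Shares 90%/30%, feature 50%/20%: 0.47/0.29 = 1.62.
- Shares 80%/40%, feature 40%/30%: 0.38/0.34 = 1.12.

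The same formula applies to columns of longer and shorter time since vaccination. If boosters go first to older people, the older share may be higher in the recently vaccinated column. Swapping the shares in the first line gives 0.32/0.44 = 0.73.

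**Step 5: within age strata.** By construction the ratio returns to its true value, 1.00 or 1.30.

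**The case against.** The best defence is that objective 6 is exploratory and descriptive, with no test or decision rule, and that Section 15.14 leaves the analyses to the SAP and the table layouts to a mock report. The protocol never calls the table unadjusted and excludes no stratification, so an SAP that is not shown could add age bands. This limits the weight of the point. It does not remove it, because the objective itself names the two factors and gives the result a comparative purpose.

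Exploratory objectives 1 to 4 also estimate CVE by severity level, including ICU admission and in-hospital death, under the adjustment in 15.14.4. That is a genuine partial safeguard. It does not cover the feature table, however, and no listed objective crosses severity with time since vaccination, although Annex 1 says CVE should be studied that way.

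Three stronger readings are tempting and are not supported:
- A reader might infer that the form rules out any later age correction, because vital signs are ticked Yes/No against a single cut-off, for example "a respiratory rate ≥ 30 per minute". Age is mandatory in Annex 4, so a Yes/No item can still be stratified or standardised by age. Only re-scoring against a different cut-off is lost.
- Section 18.3 provides for special consent procedures "or for children (assent"), and a reader might conclude that the fixed cut-offs distort the comparison for paediatric patients. The documents give no age norms and no paediatric ICU numbers, so this cannot be shown.
- A reader might infer that patients longest since vaccination must be older and sicker. The prioritisation in Section 17 refers to the period of limited supply, and the booster programmes described in Sections 8 and 13 can reverse the pattern for time since last dose.

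**Conclusion.** The point holds as a risk of confounding, not as a certain bias in a known direction. As worded, objective 6 and Section 15.9.4 can produce a vaccinated-versus-unvaccinated comparison in which age and comorbidity appear as enhanced disease or mask it. Under the assumed values above, the no-VAED ratio runs from about 1.06 to 1.6 for a feature that rises with age and from about 0.75 to 0.91 for one that falls with age; in one scenario a true 1.30 is reduced to 0.98.

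The protocol supports the link between vaccination and age or comorbidity. The link between ICU features and age, among patients already selected by ICU admission, is assumed; without it the ratio is 1.00. Because the objective is exploratory, the weight is moderate. The change is still worth making, because the question is one of safety and the needed covariates are already collected.

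**What to change.** In objective 6 and Section 15.9.4, state that the Annex 1 features are described within age bands, or as prevalences by exposure and time since vaccination standardised for age and chronic conditions, or both, with calendar period added where numbers allow. Age, chronic conditions and admission date are already mandatory in Annex 4. Add that the unstandardised table is not read as evidence for or against VAED.

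The cost is a sentence or two of protocol text and one more table. The drawback is sparse cells in some strata, so bands may have to be broad.

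As an optional extra, the form could record the measured vital-sign value beside the Yes/No tick. The main fix does not depend on it, and it requires no change to any cut-off.
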